## Synopsis of Protocol

### **Preparation (approximately 4-6 months)**

[figure not shown]
- Submission of protocol to Dana-Farber/Harvard Cancer Center IRB (MGH and BIDMC cancer centers are part of the DF/HCC)
- Finalization of all materials, including electronic surveys (REDCap) and exit interview guide
- Training of the interventionist on the adapted intervention (see Study Team Structure)
- Registration on clinicaltrials.gov

### **Recruitment (approximately 4 months)**

- Participant recruitment (see Recruitment and Retention Plans)

**Intervention, exit interviews, and three survey assessments (26 months)**: The total length of participation for each enrolled subject will be approximately 5 months. Mind-body groups are anticipated to last 8 weeks (2 months), which is the duration of the original Relaxation Response Resiliency Program (3RP); however, this will be informed by the earlier intervention refinement phase from the Aim 1 study. A timeline for the pilot RCT (N=64) is presented below.

- A baseline assessment (T1) consisting of a survey with proposed self-report measures. We will also conduct a chart review to measure indices of healthcare engagement (see Outcome Measures, Section 4.3)
- Randomization to either 8-week arm (full descriptions in Narrative Study Description, 4.2.a)
  - (1) adapted group mind-body intervention, or
  - (2) treatment as usual (referral for cancer support group through SurvivorJourneys)
- Post-intervention assessment (T2) consisting of the survey, our chart review of healthcare engagement, and an exit interview
  - Exit interviews will take place within 1 week post-intervention (see Research Strategy, Measures, Aim 2 Primary Outcomes)
- 3-month follow-up assessment (T3) consisting of the survey and our chart review of healthcare engagement

### **Analysis and reporting of primary outcomes (feasibility and acceptability) and exploratory outcomes (12 months)**

- Cleaning of survey data
- Transcription of exit interviews
- Quantitative analyses (see Section 4.4., Statistical Design and Power)
- Qualitative analyses (see Section 4.4., Statistical Design and Power)
- Report of findings on clinicaltrials.gov
- Manuscript and grant preparation (see Research Strategy, Table 3: Planned Deliverables)

Mind-Body Resiliency Intervention for Fear of Cancer Recurrence

NCT04876599

Prepared 8/18/2023

For the Pilot RCT, the primary outcomes are feasibility and acceptability. Our statistical design accounts for use of mixed methods (qualitative and quantitative) to obtain a comprehensive understanding of the feasibility and acceptability of the intervention content and procedures. While we do not expect differences in findings due to sex, we will consider the influence of sex in the interpretation of results.

**Qualitative exit interviews** will undergo transcription and content analyses. Thematic content analysis of transcribed audio will be conducted. Themes and codes will be theoretically-driven by Uncertainty in Illness Theory and the 3RP theoretical model, coded by two coders, iteratively revised until reaching thematic saturation, and discrepancies reconciled by a third coder until acceptable reliability is achieved. Analyses and interpretations will take into account (1) condition assignment (intervention vs. treatment as usual) and (2) the group structure of the intervention condition.

- Anticipated themes will assess multiple indicators of feasibility and acceptability, including program expectations, recommendations, and perceived changes (positive, negative, severity of fear of recurrence, and healthcare engagement). Participants randomized to the intervention condition will also be asked about each mind-body skill taught (e.g., perceived benefits, challenges, barriers, any modifications made).

**Quantitative analyses** will be conducted with SPSS software to assess feasibility and acceptability. Quantitative data (e.g., % enrollment, number of intervention sessions attended, and Likert-type ratings of satisfaction) will be tested for normality (i.e., skew<3.0 and/or kurtosis<8.0) and summarized using appropriate descriptive statistics (means, medians, frequencies).

- Feasibility will be indicated if  $\geq 70\%$  of participants are retained at each follow-up assessment. Secondary metrics of feasibility include attendance (a priori benchmark  $\geq 75\%$  attend 6/8 of the treatment sessions), the ratio of eligible participants who enrolled, and interventionist fidelity.
- Acceptability will be assessed by computing frequencies of post-session surveys. A threshold of 80% ratings of “high satisfaction” will indicate acceptability.

**Exploratory longitudinal analyses** will examine within-subject patterns in FOR, resiliency, and healthcare engagement self-report measures across all three assessments (baseline, post-interventions, 12-weeks post-interventions). Consistent with guidelines for clinical trials, missing data patterns will be assessed at each timepoint and if appropriate will undergo proper handling (e.g., multiple imputation).

- With guidance from biostatistics consultant [name], [name] will conduct adjusted and unadjusted general and generalized linear mixed effects models with repeated measures on FOR (Model 1), resiliency (Model 2), and healthcare engagement (Model 3).
- Adjusted analyses will include any potential covariates correlated with FOR and/or healthcare engagement at alpha=.10.
- For modeling FOR, we will use FCRI scores (continuous, which will be modeled by the general linear mixed effects model, and dichotomized at clinical cut-off, which will be modeled by the generalized linear mixed effects model [i.e., mixed effects logistic modeling]).
- For modeling healthcare engagement, we will use MEPS scores; any discrepancies between MEPS and EMR data will be discussed with [name] and reconciled. General linear mixed effects modeling and generalized linear mixed effects model (i.e., mixed effects logistic modeling) will be used for continuous and categorical variables, respectively.
- Potential intermediary variables will be explored.
- Findings will be interpreted with caution and an understanding that the primary outcomes of the pilot RCT are feasibility and acceptability.

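### Does the undefined reconciliation of MEPS and medical-record data put the healthcare-engagement model at risk?

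*SAP*

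**What the plan says.** The SAP's Exploratory longitudinal analyses section opens by stating that the analyses "will examine within-subject patterns in FOR, resiliency, and healthcare engagement self-report measures across all three assessments". Its healthcare-engagement bullet then names the modelled measure and adds a data-handling step: "For modeling healthcare engagement, we will use MEPS scores; any discrepancies between MEPS and EMR data will be discussed with [name] and reconciled". The next sentence assigns linear and logistic mixed models, which "will be used for continuous and categorical variables, respectively". The section closes with a limit on how far the results will be pressed: "Findings will be interpreted with caution and an understanding that the primary outcomes of the pilot RCT are feasibility and acceptability".

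The medical-record data come from chart review. At baseline the Protocol synopsis says: "We will also conduct a chart review to measure indices of healthcare engagement". It points to Section 4.3 for those outcome measures and to Section 4.4 for the quantitative analyses; neither section is in the public text. Survey and chart review are paired again after the intervention (T2) and at the three-month follow-up (T3).

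**The concern.** To reconcile two sources can mean three things: changing the self-report to match the record, changing the record entry, or noting and explaining the difference. The SAP does not choose among them. It does not define a discrepancy, say which source prevails, or say whether the original value is kept. Nothing in the available text says that whoever decides is unaware of treatment arm.

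Under the first meaning, an outcome value could be edited individually once arm is known. Edits that ran more in one direction at one time point would distort the within-subject pattern. Edits that differed between arms would distort any arm comparison. The modelled variable would also become a mixture of self-report and adjudicated data, at odds with how the section describes it. The contrast with the SAP's interview coding is noticeable, since there it specifies two coders, a third to settle differences, and a reliability criterion.

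**Working it through.** The plan states no figure that depends on this point, so there is none to reproduce. The check is a reading of the passages together, with a simple count of scope.

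**1. Which variable is modelled?** The engagement bullet makes MEPS the model input. The opening sentence of the section describes the engagement measures as self-report. Replacing MEPS values with chart data would fit poorly with both. Leaving MEPS as reported, and using the discussion to understand disagreements, fits both. The wording does not prove the second reading, but it favours it.

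**2. What follows under each meaning of reconcile?**

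| Meaning | Effect on the MEPS model |
|---|---|
| Difference noted or explained only | None |
| Chart entry corrected | None, because MEPS is what is modelled |
| MEPS score changed | Possible distortion by time point, and by arm if an arm contrast is fitted |

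Only one of the three does harm, and it is the one that sits worst with the surrounding text.

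**3. Is an arm contrast at stake?** The section speaks of within-subject patterns over three assessments. It states no arm-by-time term. Bias by arm therefore needs two things that the SAP does not state: that scores are edited, and that this model compares arms.

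**4. How many values could be exposed?** Inputs: the Protocol synopsis gives the sample size ("A timeline for the pilot RCT (N=64) is presented below") and three paired assessments. The SAP's feasibility benchmark is that at least 70% "of participants are retained at each follow-up assessment".

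- All assessments complete: 64 x 3 = 192 pairs.
- At the benchmark: 0.70 x 64 = 44.8, so 45 at each follow-up. With all baselines present, 64 + 45 + 45 = 154 pairs.

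The baseline pairs belong in the count. Although the synopsis lists "Randomization to either 8-week arm" after the baseline assessment, what matters is when discrepancies are settled, and neither document dates that. The synopsis puts survey cleaning in the final analysis phase, so baseline discrepancies could also be settled after randomization. These counts are ceilings on what could be examined. Without a discrepancy rate, an edit size or a MEPS variance, no bias can be derived from them.

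**5. What else depends on MEPS?** The primary and secondary feasibility metrics are retention, attendance, the share of eligible people who enrol, and interventionist fidelity. Acceptability rests on satisfaction ratings. None of these uses MEPS or chart data.

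**The case for a change.** The strongest case for a change is that it would be cheap. One or two sentences would say whether MEPS can be edited and by whom. If the sponsor never meant to edit scores, the sentences would merely confirm it; if it did, a rule is needed. Cautious interpretation does not tell a reader whether the analysed values are self-report or adjudicated. There is also a possible knock-on effect: covariates for the adjusted models are screened at alpha = .10 on correlation with fear of recurrence, engagement or both, so edited MEPS values could affect which covariates enter.

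The silence itself stands, and so does the low cost. Three things weaken the demand.

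- The available protocol text is a synopsis that sends the reader elsewhere for the engagement measures. Section 4.3 is a natural home for such a rule, so the silence can be asserted only of the text at hand.
- The person to be consulted has been removed from the public copy, so whether that person is independent of intervention delivery cannot be judged.
- There is no single correct rule to impose. Modelling the self-report untouched is defensible. So is a written rule applied without knowledge of arm, with unreconciled scores as a sensitivity analysis. The available text does not describe the content of MEPS or of the chart indices, so it cannot show which source should prevail.

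The covariate point is one more exploratory consequence of the same condition, that scores are edited, and adds no separate risk. Nor need readers be unable to tell self-report from recorded care: that would require the chart indices to go unreported, and the SAP's sentence on continuous and categorical variables may well cover them.

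**Conclusion.** The SAP leaves a detail open, but the plan does not need to change. The effect is zero if MEPS is modelled as reported, which is the reading that best fits the SAP's own words. If scores were edited, the effect would be confined to one exploratory model in a 64-person pilot, would reach an arm comparison only if one were fitted, and cannot be sized from the documents. The ceiling of 192 pairs (154 at the retention benchmark) describes scope only. The conclusions on feasibility and acceptability are the same either way.

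This rests on two assumptions. The first is that the analysts do what is usual: keep the original responses, correct only demonstrable entry errors, and report how disagreements with the record were handled. The second is that the healthcare-engagement results are presented as exploratory, as the SAP says they will be. If a report of this trial gave an arm effect on engagement as a main result, it would be fair to ask then how MEPS and chart data were reconciled.

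### Healthcare engagement is charted at all three assessments, but the SAP specifies no model for the chart data; the only planned engagement estimate comes from self-reported MEPS scores

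*SAP*

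**What the plan says.** **Collection.** The protocol synopsis, in the assessment list that follows the recruitment heading, schedules chart review three times:

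- Baseline (T1), in addition to the survey: "We will also conduct a chart review to measure indices of healthcare engagement".
- Post-intervention (T2): "Post-intervention assessment (T2) consisting of the survey, our chart review of healthcare engagement, and an exit interview".
- Follow-up (T3): "3-month follow-up assessment (T3) consisting of the survey and our chart review of healthcare engagement".

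The synopsis refers to an outcome-measures section (4.3) for detail. That section is not in the documents available, so the indices themselves cannot be seen.

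**Analysis.** The SAP paragraph on exploratory longitudinal analyses sets its subject as "within-subject patterns in FOR, resiliency, and healthcare engagement self-report measures across all three assessments". Its healthcare engagement bullet then names the outcome: "For modeling healthcare engagement, we will use MEPS scores". Chart data appear once, in the same bullet: "any discrepancies between MEPS and EMR data will be discussed with" a named colleague and reconciled. The bullet closes by assigning linear and logistic mixed models to continuous and categorical variables, which it does not name. On missing data the SAP says that "missing data patterns will be assessed at each timepoint and if appropriate will undergo proper handling (e.g., multiple imputation").

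**The concern.** The trial collects engagement in two ways at the same three time points, and the plan turns only one of them into an estimate. That one is the more exposed of the two.

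One arm attends an eight-week mind-body group; the other receives usual care with a referral to a support group. Neither document mentions blinding, but participants can hardly be unaware of which they received. Under the SAP, exit interviews also cover perceived change in healthcare engagement. The synopsis places them within a week of the end of the intervention, and so before T3. A participant who reports on their own engagement in that setting may report what the programme encouraged.

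MEPS is also observed only where a survey is returned. A chart index needs neither the participant's report nor the survey, provided the chart may be reviewed.

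At stake is what the pilot teaches about engagement as an endpoint for later work. If self-report shifted and charts did not, that would be among the most useful findings available. A process that reconciles both sources into one score could remove it from view.

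**Working it through.** There is no stated figure to reproduce: the documents give no power, effect size or SD for the engagement analysis. The check is mainly a comparison of texts, followed by a calculation for scale.

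**1. Collection against analysis**

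| Source of engagement data | Collected | Role in the SAP |
|---|---|---|
| Self-report (MEPS) | T1, T2, T3 survey | Outcome of Model 3 |
| Chart review (taken to be the SAP's EMR data) | T1, T2, T3 | Compared with MEPS, discrepancies reconciled; no variable defined, no model specified |

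**2. What reconciliation can and cannot supply.** Where both sources exist, it yields at most one corrected MEPS value. Where MEPS is missing, there is nothing to reconcile. In neither case does it give a chart-based comparison of the arms. No rule says which source prevails or whether the score changes.

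**3. Scale of missing surveys.** Inputs: N = 64 (protocol synopsis) and retention of at least 70% at each follow-up (SAP, feasibility bullet).

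- Smallest number meeting the benchmark: 0.70 × 64 = 44.8, so 45 (45/64 = 70.3%).
- Largest loss compatible with it: 64 − 45 = 19.

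This is a bound, not a forecast. It treats retained as survey returned, which the SAP does not define.

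**4. Precision at one follow-up visit.** Assumptions: 1:1 allocation (not stated in the documents), chart data for all 64, and observed data only. With m participants in total, the 95% half-width for a between-arm mean difference, in SD units, is 1.96 × √(4/m). The ratio of standard errors against the full sample is √(64/m).

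| Retention | m | Half-width (SD) | SE ratio |
|---|---|---|---|
| 100% (charts for all) | 64 | 1.96 × √(4/64) = 0.49 | 1.00 |
| 90% | 58 | 1.96 × √(4/58) = 0.51 | 1.05 |
| 80% | 52 | 1.96 × √(4/52) = 0.54 | 1.11 |
| 70% | 45 | 1.96 × √(4/45) = 0.58 | 1.19 |

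The gain in precision is modest even at the benchmark. The stronger argument is that a chart index does not depend on report or survey return, and the documents do not allow that benefit to be sized.

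**5. Look-back.** T1 to T2 spans about 8 weeks and T2 to T3 about 12 weeks. Counts taken simply between visits would cover unequal periods, so a chart model needs a fixed window before each assessment.

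**The case against.** The other side has good points, and several stand.

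- **Completers only.** A reader might infer that the engagement result rests on survey completers alone. The documents do not support that. Repeated-measures mixed models use every available visit, so someone who misses one survey still contributes the others, and multiple imputation is named as an option. What remains is that missed visits rest on missing-data assumptions, which chart data could reduce or help test.
- **Charts ignored.** A reader might also infer that chart data have no influence, or that a divergence would leave only the self-report change on record. That goes too far: the reconciliation clause gives charts some bearing on MEPS values. But an undefined reconciliation supplies no second estimate.
- **Never modelled.** This is slightly too firm, because the closing sentence on continuous and categorical variables names none. Still, it sits in the MEPS bullet, and the paragraph's stated scope is "healthcare engagement self-report measures across all three assessments". A chart outcome would have to be read into it.
- **Charts are not bias-free.** This stands. The indices are not defined in the available text, nothing is said about blinding of chart reviewers, and care received elsewhere is missed. Access to non-responders' charts depends on consent terms, which cannot be seen here.
- **Exploratory status.** The SAP calls for cautious interpretation, and self-report is a legitimate choice of exploratory endpoint. This limits the weight of the point but does not remove it.

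It would also be tempting to require that both measures agree before any change is claimed. That would impose a decision rule on an exploratory analysis that makes no such claim. If there were no effect and the measures were independent (an assumption), directions would agree about half the time by chance (0.5 × 0.5 + 0.5 × 0.5 = 0.5).

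**Conclusion.** The point holds in a limited form. Chart-review engagement is scheduled at T1, T2 and T3, and the SAP specifies no model for it. The only planned engagement estimate uses self-reported MEPS scores, possibly altered by a reconciliation with no stated rule. That estimate is open to reporting bias, on the inference that participants know their arm, and it relies on missing-data assumptions wherever surveys are missed.

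The bias cannot be quantified from the documents. The 19 of 64 figure is only the largest loss the benchmark tolerates, and the precision figures rest on 1:1 allocation and full chart access. Nothing here touches the primary feasibility and acceptability outcomes. This is a cheap improvement to an exploratory analysis, not an error that undermines the trial.

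**What to change.** Add an exploratory Model 3b to the SAP:

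- **Outcome:** the chart-review engagement indices at T1, T2 and T3, defined in the SAP or by reference to the outcome-measures section.
- **Population:** all randomised participants whose charts may be reviewed, whether or not the survey was returned.
- **Window:** a look-back of equal length before each assessment.
- **Model:** a repeated-measures mixed model by arm, with a link suited to the index. The engagement bullet names only linear and logistic forms, so an index that is a count needs a count model.
- **Reporting:** beside Model 3 fitted to MEPS as reported, before any reconciliation. Describe agreement or divergence between the two, without a rule that they must agree.

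The cost is a short SAP addition, the work of defining the indices and window, and one extra exploratory model on data whose collection is already scheduled. The downside is that charts miss care outside the reviewed systems, so the two results may differ for that reason alone; the report should say so.
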